Title: Optical Coherence Tomography Predictors of Functionally Significant Side Branch Compromise after Provisional Main Vessel Stenting in Bifurcation Lesion Assessed by Fractional Flow Reserve (ORBID-FFR)

PI: [name]

NCT03115580

Document Date: January 19, 2017

 Mount Sinai	Protocol Title:	Optical Coherence Tomography Predictors of Functionally Significant Side Branch Compromise after Provisional Main Vessel Stenting In Bifurcation Lesions Assessed by Fractional Flow Reserve (ORBID – FFR)
	Principal Investigator Name/Contact Info:	[name]./ [name]/ [contact]
	Primary Contact Name/Contact Info	[name] /[name] / [contact] [name] /[name] [contact]
	Date Revised:	January 19, 2017
	Study Number:	HSM# 16-00041/ GCO#1: 16-0204(0001)

MSSM Protocol Template HRP-503a

Instructions:

1. Prepare a document with the following sections. Note that, depending on the nature of your research, certain sections below may not be applicable. Indicate N/A as appropriate, explaining where possible.
2. For any items described in the sponsor's protocol, grant application or other source documents submitted with the application, you may reference the title and page numbers of these documents rather than cutting and pasting into this document. **Do NOT refer to any derived documents, such as the Sample Consent document, or other internal documents required with the submission.**
3. If you reference page numbers, attach those pages to this protocol.
4. When you write a protocol, keep an electronic copy. You will need to modify this copy when making changes.

Brief Summary of Research (250-400 words):

Protocol Title: Optical Coherence Tomography Predictors of Functionally Significant Side Branch Compromise after Provisional Main Vessel Stenting in Calcific Coronary Artery Disease (CAD) Assessed by Fractional Flow Reserve (ORBID-FFR)

This is a single-center, randomized study in patients with stable coronary artery disease.

1) Objectives:

Research Question:

To analyze the incidence of SB compromise after provisional main vessel stenting in calcified bifurcation lesions of CAD patients, determine the incidence and OCT predictors of functionally significant SB stenosis defined as FFR ≤ 0.8 and to compare the FFR values with 3D-OCT measurements of jailed SB ostium after MV stenting.

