 Mount Sinai	Protocol Title:	Optical Coherence Tomography Predictors of Functionally Significant Side Branch Compromise after Provisional Main Vessel Stenting In Bifurcation Lesions Assessed by Fractional Flow Reserve (ORBID – FFR)
	Principal Investigator Name/Contact Info:	[name]./ [name]/ [name]
	Primary Contact Name/Contact Info	[name] /[name] / [name] [name] /[name] [name]
	Date Revised:	January 19, 2017
	Study Number:	HSM# 16-00041/ GCO#1: 16-0204(0001)

Data analysis and Statistical methods:

T-test will be used. OCT off-line image analysis. For the accurate characterization of bifurcation lesions, OCT images will be analyzed systematically at 1 mm intervals according to previously validated criteria for plaque characterization using the St. Jude Medical Offline Review Workstation as we described previously. In addition, three-dimensional OCT software (QAngio OCT, Medis) will be used to obtain the information for the side branch ostium from a single main branch pullback as described recently in a validation of cut plane analysis (Figure 2). We will also perform three-dimensional quantitative coronary angiography (3D-QCA) using QAngio XA 3D software (Medis) to obtain the measurements of bifurcation angles, stenosis, and references. This software is dedicated to bifurcation lesions and has shown to provide highly accurate assessment of lesion dimensions and geometry based on 3D reconstruction of bifurcation lesions. Offline analysis of side branch for impingement of the ostium of SB leading to acute loss in SB diameter, area, carina shift and plaque shift will be performed and 3D-OCT parameters will be correlated with SB FFR measurements.

 Mount Sinai	Protocol Title:	Optical Coherence Tomography Predictors of Functionally Significant Side Branch Compromise after Provisional Main Vessel Stenting In Bifurcation Lesions Assessed by Fractional Flow Reserve (ORBID – FFR)
	Principal Investigator Name/Contact Info:	[name]./ [name]/ [contact]
	Primary Contact Name/Contact Info	[name] /[name] / [contact] [name] /[name] [contact]
	Date Revised:	January 19, 2017
	Study Number:	HSM# 16-00041/ GCO#1: 16-0204(0001)

[figure not shown]

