Protocol Title:	Optical Coherence Tomography Predictors of Functionally Significant Side Branch Compromise after Provisional Main Vessel Stenting In Bifurcation Lesions Assessed by Fractional Flow Reserve (ORBID – FFR)
Principal Investigator Name/Contact Info:	[name]./ [name]/ [contact]
Primary Contact Name/Contact Info	[name] /[name] / [contact] [name] /[name] [contact]
Date Revised:	January 19, 2017
Study Number:	HSM# 16-00041/ GCO#1: 16-0204(0001)

informed consent document, a copy will be placed in the subject's chart and the original copy will be stored in a secure location in the research office.

b) Inclusion and Exclusion Criteria

1. General inclusion criteria. Subjects will be enrolled in the study, if **ALL** of the following criteria are met

- All patients over 18 years of age presenting with stable coronary artery disease.
- Patients must have a clinical indication for coronary intervention.
- Creatinine Kinase Myocardial-Band Isoenzyme (CK-MB) must be less than or equal to the upper limit of lab normal (ULN) value within eight hours prior to the procedure

2. Angiographic inclusion criteria. Subjects will be enrolled in the study, if **ALL** of the following criteria are met:

- The target lesion must be a *de novo* calcified bifurcation coronary lesion that hasn't been previously treated with any interventional procedure for which provisional main vessel stenting strategy is planned after reviewing angiogram.
- The target vessel must be a native coronary artery with
 - a) stenosis $\geq 70\%$ and $<100\%$, or
 - b) Stenosis $\geq 50\%$ and $<70\%$ with evidence of clinical ischemia via positive stress test, or FFR ≤ 0.8 , or IVUS or OCT minimal lumen area $\leq 4.0 \text{ mm}^2$.
- The target lesion should have SB DS 30 - 70%.
- The target main vessel reference diameter must be $\geq 2.5 \text{ mm}$ and $\leq 4.0 \text{ mm}$.
- The SB reference diameter must be $> 2 \text{ mm}$ by coronary angiogram.
- The target vessel must have a Thrombolysis in Myocardial Infarction (TIMI) flow grade 3 at baseline.

Protocol Title:	Optical Coherence Tomography Predictors of Functionally Significant Side Branch Compromise after Provisional Main Vessel Stenting In Bifurcation Lesions Assessed by Fractional Flow Reserve (ORBID – FFR)
Principal Investigator Name/Contact Info:	[name]./ [name]/ [contact]
Primary Contact Name/Contact Info	[name] /[name] / [contact] [name] /[name] [contact]

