Date Revised:	January 19, 2017
Study Number:	HSM# 16-00041/ GCO#1: 16-0204(0001)

General exclusion criteria: Patient will not be enrolled in the study if ANY of the following criteria are present in the patient.

- Patients with ostial left main artery lesions or ostial right coronary artery lesions
- Female patients with child bearing potential not taking adequate contraceptives or currently breastfeeding
- Known allergy to acetylsalicylic acid or clopidogrel.
- Planned surgery within 12 months.
- History of bleeding diathesis
- Major surgery within 15 days
- Life expectancy < 12 months.
- Patients with kidney dysfunction (CrCl<30)

c) Number of Subjects

One hundred and fifty (150) consecutive patients with lesions requiring PCI of main vessel with drug eluting stent implantation for the treatment of stable CAD will be included in the study.

d) Study Timelines

This is a randomized study with one visit and no clinical follow-ups.

e) Study Endpoints

The primary endpoint is SB compromise defined as SB DS \geq 70%, or dissection or TIMI < 3.

The secondary endpoints

- SB FFR after main vessel stenting and its correlation with OCT imaging parameters before PCI
- OCT predictors of SB TIMI flow reduction after main vessel PCI
- Off-line analysis of SB stenosis by 3D-OCT and its correlation with FFR; correlation between 3D-QCA measurements, 3D-OCT, and FFR data.

Protocol Title:	Optical Coherence Tomography Predictors of Functionally Significant Side Branch Compromise after Provisional Main Vessel Stenting In Bifurcation Lesions Assessed by Fractional Flow Reserve (ORBID – FFR)
Principal Investigator Name/Contact Info:	[name]./ [name]/ [contact]
Primary Contact Name/Contact Info	[name] /[name] / [contact] [name] /[name] [contact]
Date Revised:	January 19, 2017
Study Number:	HSM# 16-00041/ GCO#1: 16-0204(0001)

- Association between calcification assessment by angiography and OCT imaging.
- FFR Device Success (ability to successfully deliver FFR wire to desired SB distal segment [n/150]).
- FFR Wire Workhorse Capability (proportion of patients [n/150] in which FFR wire able to serve as rail to deliver additional interventional devices to target SB lesion).

f) Procedures Involved in the Human Research

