Patients in both groups will undergo (standard of care) a percutaneous coronary intervention (PCI), also known as coronary angioplasty, is a nonsurgical technique for treating obstructive coronary artery disease, including unstable angina, acute myocardial infarction (MI), and multivessel coronary artery disease (CAD) with stent implantation according to current standards of care. Lesion preparation including lesion pre-dilation, scoring or sculpting balloon angioplasty, and use of atherectomy (a minimally invasive endovascular surgery technique for removing atherosclerosis from blood vessels within the body.) and protection devices will be performed at the operator's discretion, followed by MV stenting.

The operator will also decide in both groups about the length and size of the implanted stent. Procedural optimization, such as post-dilation or additional stent implantation will be performed based only on the angiographic findings, according to the discretion of the operator.

The Pre and post stenting OCT + FFR for side branch are the research procedures.

OCT pullback will be performed after lesion preparation before stenting (OCT-PRE) and after PCI (OCT-POST). FFR measurement in the side branch will be performed, if the coronary angiogram shows SB DS < 70%, TIMI grade 3 flow and no dissection in the side branch.

To perform FFR measurements, the pressure wire will be passed through the struts of the MV stent into the SB and FFR will be measured at least 5 mm distal to the jailed SB stenosis. Adenosine will be infused through the

Protocol Title:	Optical Coherence Tomography Predictors of Functionally Significant Side Branch Compromise after Provisional Main Vessel Stenting In Bifurcation Lesions Assessed by Fractional Flow Reserve (ORBID – FFR)
Principal Investigator Name/Contact Info:	[name]./ [name]/ [contact]
Primary Contact Name/Contact Info	[name] /[name] / [contact] [name] /[name] [contact]
Date Revised:	January 19, 2017
Study Number:	HSM# 16-00041/ GCO#1: 16-0204(0001)

femoral vein at least 140 µg/kg per minute to induce maximal coronary blood flow.

g) Specimen Banking

Not Applicable

h) Data Management and Confidentiality

Confidentiality of subject medical information will be ensured by providing unique identifiers (Subject ID) for data transmitted from the enrolling centers to St. Jude Medical Center. Designated representatives will not receive identifiable subject information.

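### 3D-OCT reads only the side-branch ostium, FFR also takes in any pressure loss further down the branch, and that downstream disease is not recorded, so the planned correlations cannot separate the two

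*Combined protocol and SAP*

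**What the plan says.** **3D-OCT.** Section 5, Data analysis and Statistical methods, uses the 3D software "to obtain the information for the side branch ostium from a single main branch pullback", and the legend of Figure 2 describes the same ostial cut-plane analysis. The research question in section 1 is "to compare the FFR values with 3D-OCT measurements of jailed SB ostium after MV stenting". This measure is ostial.

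**The endpoint.** Section 5 e) does not say ostial. It lists "Off-line analysis of SB stenosis by 3D-OCT and its correlation with FFR; correlation between 3D-QCA measurements, 3D-OCT, and FFR data".

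**Angiographic stenosis.** The entry criterion in 5 b) reads "The target lesion should have SB DS 30 - 70" (per cent). In 5 e), "The primary endpoint is SB compromise defined as SB DS" of 70% or more, or dissection, or TIMI flow below 3. The 3D-QCA text lists stenosis among its outputs. None of these names a segment of the branch.

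**FFR.** Under 5 f), "FFR will be measured at least 5 mm distal to the jailed SB stenosis". No maximum distance, wire pullback or recording of sensor position is stated. The device-success endpoint in 5 e) refers to the distal segment of the branch. FFR is measured only where SB stenosis is below 70%, flow is TIMI 3 and there is no dissection.

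**Disease beyond the ostium.** In the readable text, nothing excludes it, records it or adjusts for it.

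**The concern.** A pressure wire reads the sum of all losses upstream of its sensor. If a branch has a narrowing between the ostium and the sensor, FFR reflects both sites while 3D-OCT sees one. Such a branch can be FFR-positive with a fairly open ostium. It is then counted as functionally significant SB stenosis after jailing, and as a failure of 3D-OCT to detect it.

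Three results depend on this: the correlations of 3D-OCT and 3D-QCA with FFR, the analyses of pre-stent OCT predictors of FFR, and the incidence of FFR ≤ 0.8 that the research question asks for. The comparison of 3D-QCA with 3D-OCT is also hard to read if the two cover different lengths of branch. Without a record of downstream disease, a weak or strong ostial correlation cannot be explained afterwards.

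**Working it through.** **1. Which segment each measure covers**

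| Measure | Segment in the plan |
|---|---|
| 3D-OCT | SB ostium |
| Entry SB stenosis | not stated; attached to the target bifurcation lesion |
| Primary-endpoint SB stenosis | not stated |
| 3D-QCA stenosis | not stated; software dedicated to bifurcations |
| FFR | everything upstream of a sensor at least 5 mm past the jailed stenosis |

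**2. One branch, for intuition.** Take a pressure-loss proxy of 1/(1−DS)² − 1, where DS is the diameter stenosis as a fraction (an assumption, not in the plan). An ostial DS of 0.25 gives 1/0.75² − 1 = 0.78. A downstream DS of 0.60 gives 1/0.40² − 1 = 5.25. FFR responds to 6.03 and 3D-OCT sees 0.78.

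**3. Illustration over many branches.** The documents give no frequency of downstream disease, so all inputs are assumptions except the 25% FFR-positive prevalence and the below-70% limit for FFR. Simulated branches: 300,000. Ostial DS ~ N(0.45, 0.15), clipped to 0–0.69. Outcome = ostial loss + downstream loss + Gaussian noise, with the noise set so that r = 0.60 when there is no downstream disease, and the FFR-positive cut set at 25%. The AUC of ostial stenosis for FFR-positive is then 0.81. A share f of branches receives downstream DS ~ U(0.30, 0.69), in three ways:

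- A: affected branches have mild ostia, N(0.25, 0.12).
- B: affected branches have the same ostia as the rest.
- C: the chance of downstream disease rises in proportion to the rank of ostial DS, with the overall share still f.

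Slope is the unadjusted ostial slope relative to its true value.

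| f | A: r, AUC, slope | B: r, AUC, slope | C: r, AUC, slope |
|---|---|---|---|
| 10% | 0.52, 0.73, 0.87 | 0.57, 0.78, 1.00 | 0.60, 0.80, 1.08 |
| 20% | 0.45, 0.68, 0.77 | 0.55, 0.76, 1.00 | 0.61, 0.81, 1.16 |
| 30% | 0.38, 0.63, 0.68 | 0.53, 0.75, 1.00 | 0.62, 0.81, 1.24 |

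FFR-positive incidence rises from 25% in every case: to 26.5, 27.8 and 29.1% under A, and to between 28 and 35% under B and C.

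Adding downstream loss as a covariate returns a relative slope of 1.00 in all nine cells. Entering plain downstream DS as a linear term gives 0.97 to 1.04.

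**4. The lipid predictor.** First, the plan's own figure. Assume two-sided α 0.05 (not stated) and 25% as the low-lipid rate. OR 2.8 gives odds 0.3333 × 2.8 = 0.9333, so p₂ = 0.4828, d = 0.2328 and mean 0.3664.

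n = [1.96√(2 × 0.3664 × 0.6336) + 0.8416√(0.25 × 0.75 + 0.4828 × 0.5172)]² / 0.2328² = 66.1. With continuity correction, (66.1/4)[1 + √(1 + 4/(66.1 × 0.2328))]² = 74.4, so 75 per group, as stated.

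Now let a share q of FFR-positive results come from downstream disease unrelated to lipid, with overall prevalence fixed. Each group rate becomes q × 0.3664 + (1−q) × p. At q = 20% the rates are 0.273 and 0.459, OR 2.26.

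| q | OR | Power at 75 per group |
|---|---|---|
| 0 | 2.80 | 80% |
| 10% | 2.51 | 71% |
| 20% | 2.26 | 60% |
| 30% | 2.04 | 48% |

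The dilution here follows from the assumption that downstream disease is unrelated to lipid.

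**The case against.** A reader might infer that the plan contradicts itself: side-branch stenosis would mean the ostium for 3D-OCT and the whole branch for entry, the stenosis endpoint, 3D-QCA and FFR. The text does not say that. It leaves the segment open, and several places lean ostial. The Background presents FFR as a test of ostial SB stenosis, and the offline analysis concerns impingement at the ostium. The entry stenosis belongs to a target lesion described as a "calcified bifurcation coronary lesion that hasn't been previously treated with any interventional procedure", and FFR is anchored to the jailed stenosis. This objection stands against the claim of contradiction. It does not remove the gap: an ostial intention neither defines a segment nor excludes downstream disease.

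A reader might also infer that the OCT associations must be biased toward zero and that 3D-QCA is favoured. Neither is established. Under C the correlation is not weakened and the slope is inflated. The plan does not say how far 3D-QCA reaches into the branch. The large losses under A come from assuming mild ostia in the affected branches.

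Two further objections stand. The affected analyses are secondary. And restricting the main analysis on post-stent stenosis would condition on a result of the intervention. The fix takes account of both.

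**Conclusion.** The concern holds as an undefined segment and an unrecorded source of pressure loss. It does not hold as a contradiction between definitions. As written, the ostial 3D-OCT measure is correlated with an FFR value that carries any loss between ostium and sensor, and nothing collected would let the two be separated.

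The size is unknown. With 10 to 30% of branches affected (assumed), the result ranges from a correlation of 0.38 in place of 0.60 to a correlation essentially unchanged with a slope 24% too steep. The direction depends on how downstream disease relates to ostial severity, which the documents do not settle. All of this rests on the additive loss proxy and error-free stenosis measurements. The sample-size figure reproduces and is not in question, and no effect on the primary endpoint is shown. This is a cheap improvement to the secondary analyses, not a flaw that undermines the trial.

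**What to change.** 1. In 5 e) and in Data analysis and Statistical methods, name the 3D-OCT endpoint as ostial, and report 3D-QCA SB stenosis for the same ostial segment, with its length fixed before the films are read.
2. From the baseline angiogram and planned 3D-QCA, record the worst SB stenosis beyond that segment. Record the distance of the FFR sensor from the ostium at the time of measurement, since it may not be recoverable later.
3. Enter baseline downstream stenosis as a covariate in the 3D-OCT and 3D-QCA versus FFR analyses and in the OCT-predictor analyses. Show this beside the unadjusted all-branch result.
4. Add a sensitivity analysis in branches free of baseline downstream disease, with the cut-off stated in advance.

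Leave the entry criterion and the primary-endpoint definition as they are, and do not restrict the main analysis on post-stent stenosis.

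Cost: one extra reading on existing films, one distance noted during the procedure and one extra model term, with no added procedure or patients. Angiographic stenosis is an imperfect measure of pressure loss (the Background cites an AUC of 0.64 for QCA), so adjustment will be partial. If downstream disease proves rare, the record will show that the unadjusted results can be taken at face value on this point.

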assessing the mechanism of side-branch compromise following intervention in bifurcation lesions. The recent development of OCT with online 3D reconstruction allows the operator to obtain a 3D visualization of the lesion and may provide a unique tool for guidance during complex bifurcation PCI and potentially improve stenting results. 3D OCT has been used to visualize jailed side branches after implantation of bioresorbable scaffolds in the main branch and develop a new classification system based on the number of SB compartments. In addition, its potential clinical application in guiding the rewiring of the distal compartment of the SB ostium (jailed with stent struts after MB stenting) to minimize the risk of floating struts was demonstrated. It is important to note that while OCT, 3D-OCT, and 3D-QCA (such as that used in the ORBID trial) are imaging modalities that can be used to answer important research questions, their wide-spread adoption in daily clinical practice has been very limited. Intravascular ultrasound (IVUS) is used more frequently as part of a PCI guidance strategy in daily clinical practice.

Fractional flow reserve (FFR) is a pressure-derived, lesion specific index used to determine the functional significance of coronary artery stenosis. Several studies showed that FFR is a safe and feasible method to assess the significance of an ostial SB stenosis after provisional stenting. Quantitative coronary angiography (QCA) has been shown to be unreliable in assessing the functional significance of SB after stent implantation in MV (the area under the curve 0.64, 41.5% sensitivity and 83.1% specificity) suggesting that treatment decisions for jailed SB should not be based on angiographic findings alone. A recent report demonstrated a better ability of post-PCI 3D-OCT to predict the functional significance for SB ostial lesions caused by a jailed SB outcome.

A previous study (ORBID) of 30 patients was done at Mount Sinai Hospital and aimed to identify the predictors of side branch (SB) ostial stenosis developed after provisional stenting of the main vessel (MV) using Optical Coherence Tomography (OCT). The study Showed that High lipid content of the MV lesion and a contralateral location of lipid in the bifurcation area may contribute to SBOS after provisional stenting.

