Figure 2. 3D quantitative coronary angiography (QCA) and cut-plane analysis of side branch ostium from the main branch OCT pullback for bifurcation PCI before (top row) and after (bottom row) stenting.

We assumed FFR (+) prevalence of either 20% or 25% based on previous studies. We also assumed that there would be a roughly equal proportion of patients with high and lipid levels.

Based on these assumptions, we will need at least 75 patients per EACH high lipid and low lipid groups to detect an odds ratio (OR) of 2.8.

Protocol Title:	Optical Coherence Tomography Predictors of Functionally Significant Side Branch Compromise after Provisional Main Vessel Stenting In Bifurcation Lesions Assessed by Fractional Flow Reserve (ORBID – FFR)
Principal Investigator Name/Contact Info:	[name]./ [name]/ [contact]
Primary Contact Name/Contact Info	[name] /[name] / [contact] [name] /[name] [contact]
Date Revised:	January 19, 2017
Study Number:	HSM# 16-00041/ GCO#1: 16-0204(0001)

The table below is showing the detectable OR we might have under different assumptions of the patient population assuming an equal proportion of high/low lipid level groups.

Prevalence of + FFR	Patients per group	Detectable OR with 80% power
0.2	50	3.7
0.2	75	2.9
0.2	100	2.5
0.25	50	3.5
0.25	75	2.8
0.25	100	2.4

a) Recruitment Methods

We will recruit patients referred to the interventional cardiologists involved on this study based on their medical history who require a PCI of the main vessel with drug eluting stent implantation for the treatment of stable CAD where impact on the side branch can be access. Patients will be undergoing a PCI using an angiography and OCT-guided strategy. Patients will be approached in the ambulatory unit before their procedure to obtain consent and review and confirm the inclusion and exclusion criteria of the protocol.

The PI and the research team will identify potential subjects based on their medical history. Potential patients will be approached in the ambulatory unit before their procedure to obtain consent and check the inclusion/exclusion criteria.

In all cases, the Principal Investigator, Sub-Investigator or member of the Research Team will discuss the research trial and informed consent document in full detail following Good Clinical Practices and HIPAA Laws. During the informed consent process, all of the potential subject's questions will be answered. Subjects will be given a copy of the signed

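### 3D-OCT and 3D-QCA are related to FFR by correlation only, which does not show how well either identifies a side branch with FFR at or below 0.8

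*Combined protocol and SAP*

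**What the plan says.** Section 1) Objectives sets a binary target: to "determine the incidence and OCT predictors of functionally significant SB stenosis defined as FFR ≤ 0.8". It adds the aim "to compare the FFR values with 3D-OCT measurements of jailed SB ostium after MV stenting", without a method.

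Section 2) Background reports the performance of QCA against FFR as "the area under the curve 0.64, 41.5% sensitivity and 83.1% specificity" and concludes that angiography alone should not drive decisions on jailed side branches. It continues: "A recent report demonstrated a better ability of post-PCI 3D-OCT to predict the functional significance for SB ostial lesions". No figure is given for 3D-OCT.

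The analysis text uses different terms. Under Data analysis and Statistical methods, "3D-OCT parameters will be correlated with SB FFR measurements", and the only named test is given as "T-test will be used", with no variables attached. Section e) Study Endpoints lists the correlation of 3D-OCT side-branch stenosis with FFR and "correlation between 3D-QCA measurements, 3D-OCT, and FFR data". No section plans an ROC curve, an AUC, a cut-off, sensitivity or specificity, or an agreement statistic.

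Section f) Procedures limits FFR to side branches with diameter stenosis (DS) below 70%, TIMI 3 flow and no dissection after stenting.

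**The concern.** The rationale is about classification: does an image measurement tell the operator that a jailed side branch is functionally significant? Correlation answers another question, namely how closely two continuous measurements move together across their whole range. It gives no error rate at the 0.8 threshold and cannot be set beside an AUC, a sensitivity or a specificity. The t-test does not fill the gap, because a difference in means between FFR groups gives no error rates either.

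At stake is how the secondary results will be read. A correlation with a small p-value could be reported as support for 3D-OCT when its discrimination is no better than the level the protocol calls unreliable for QCA. A narrower issue concerns 3D-OCT against 3D-QCA. Where both measure the same quantity, correlation does not detect a systematic offset.

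**Working it through.** **Inputs from the documents.** N = 150 (section c). FFR-positive prevalence: "We assumed FFR (+) prevalence of either 20% or 25% based on previous studies" (sample-size text). QCA benchmark: AUC 0.64, sensitivity 41.5%, specificity 83.1% (section 2). FFR is measured only in the subset described in section f; its size is not given.

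**Assumptions.** Two-sided 5% level (the plan states none). The 20-25% prevalence applies to all patients with FFR. FFR is available in 105 to 150 patients. The gate for FFR is the complement of the primary endpoint, so 105 corresponds to a 30% rate of side-branch compromise (150 × 0.70).

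**The plan's own figure.** The sample size concerns lipid groups, not imaging accuracy, but it is the only calculation given. Take 25% as the low-lipid rate. OR 2.8 then gives odds 0.3333 × 2.8 = 0.9333 and p₂ = 0.4828. The pooled-variance formula at 80% power gives

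n = [1.96√(2 × 0.3664 × 0.6336) + 0.8416√(0.1875 + 0.2497)]² / 0.2328² = 66.1,

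and the continuity correction raises this to 74.4, so 75 per group, as stated. If 20-25% is the low-lipid rate, overall prevalence is higher and the AUC intervals below would be somewhat narrower.

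**Step 1: what a significant correlation implies.** The critical value is r = t/√(n − 2 + t²). With n = 150 and t = 1.976, r = 1.976/√(148 + 3.905) = 0.160. For r = 0.2, t = 0.2√(148/0.96) = 2.48, p = 0.014.

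The matching AUC was found by simulating a bivariate normal pair and splitting FFR at the 20% or 25% most severe values:

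| r | AUC |
|---|---|
| 0.2 | 0.60 |
| 0.3 | 0.64-0.65 |
| 0.5 | 0.74-0.75 |
| 0.6 | 0.79-0.80 |

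So r of 0.2 to 0.3 is significant but sits at AUC 0.60-0.65.

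**Step 2: precision of an AUC.** Hanley-McNeil: SE² = [A(1 − A) + (n₁ − 1)(Q₁ − A²) + (n₀ − 1)(Q₂ − A²)]/(n₁n₀), with Q₁ = A/(2 − A) and Q₂ = 2A²/(1 + A). For A = 0.64, n₁ = 30, n₀ = 120: Q₁ = 0.4706, Q₂ = 0.4995, SE² = (0.2304 + 1.769 + 10.70)/3600 = 0.00353, SE = 0.0594, half-width 1.96 × 0.0594 = 0.116.

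| Patients with FFR | FFR-positive | Half-width, AUC 0.64 | Half-width, AUC 0.80 |
|---|---|---|---|
| 150 | 30 (20%) | 0.116 | 0.100 |
| 150 | 38 (25%) | 0.106 | 0.090 |
| 105 | 21 (20%) | 0.139 | 0.120 |
| 105 | 26 (25%) | 0.128 | 0.109 |

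For sensitivity and specificity near the cited values, 1.96√(p(1 − p)/n) gives about ±16 to 18 points on 30-38 positives and ±7 points on 112-120 negatives.

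**Step 3: comparing two AUCs in the same patients.** Take 0.80 v 0.64 with all 150 patients. Power is Φ(0.16/SE_diff − 1.96), where SE_diff² = s₀² + s₁² − 2ρs₀s₁. It is 53-61% if the two AUC estimates are uncorrelated (ρ = 0), 68-77% at ρ = 0.3 and 82-89% at ρ = 0.5.

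**Step 4: effect of the FFR gate.** As an illustration, give two methods the same correlation of 0.6 with severity (AUC 0.79-0.80), with independent errors, and exclude the worst 10-30% on the angiographic one. The 3D-OCT AUC becomes about 0.77-0.79 and the angiographic AUC about 0.71-0.75. A looser link between the gate and 3D-QCA gives a smaller gap.

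**Step 5: agreement.** Suppose percent stenosis has SD 12, one method reads 15 points higher, and the error SD is 6 (all assumed). Then r = 12/√(144 + 36) = 0.89, but the limits of agreement are 15 ± 1.96 × 6, about +3 to +27 points.

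**The case against.** The strongest reply is that the plan does not ask whether 3D-OCT beats angiography. A reader might infer that it does, because section 2 sets QCA accuracy beside a report favouring 3D-OCT. The documents do not support that: no objective, endpoint or hypothesis claims superiority. The benchmark is also for QCA, not stated to be 3D-QCA, and comes from other patients. This stands.

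Correlation is not empty. Step 1 itself maps r to AUC under a distributional assumption, and binary FFR is used elsewhere: the objectives seek its OCT predictors, and the sample size rests on an odds ratio for it. This stands too. The gap is confined to how 3D-OCT and 3D-QCA are related to FFR.

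A reader might also infer that the two imaging methods measure the same lengths and areas, so that agreement is a general problem. The statistical methods assign bifurcation angles, stenosis and references to 3D-QCA and the side-branch ostium to 3D-OCT; only stenosis clearly overlaps. Nor does a proportional under-reading of area matter to percent area stenosis if lesion and reference are affected alike. Agreement with FFR, a pressure index on another scale, is not meaningful.

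Finally, the FFR gate restricts AUC as well as r, so it is no argument for AUC over correlation. It can also tilt a paired comparison against 3D-QCA (step 4). Together with the power in step 3, this rules out presenting that comparison as a superiority test.

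What remains unanswered is that the plan sets a threshold and cites accuracy measures, then specifies none for these measurements.

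**Conclusion.** The point holds as a mismatch between the binary target and accuracy framing in sections 1 and 2 and the correlation-only analysis in the statistical methods and section e. The planned analysis could give a clearly significant r of 0.2 to 0.3 with an AUC of only about 0.60-0.65. That mapping rests on bivariate normality and 20-25% FFR-positive.

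The point concerns secondary endpoints. It does not touch the primary endpoint, the sample size or study conduct, and it does not show that the trial fails a stated superiority aim. An accuracy analysis is feasible as estimation, with AUC half-widths of about 0.09-0.12 with FFR in all 150 patients and up to about 0.14 with 105. A firm conclusion about which method is better is not assured at this size.

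**What to change.** Add to the statistical methods, for the secondary endpoint:

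- For 3D-OCT and for 3D-QCA, report the AUC against FFR at or below 0.8 with a 95% CI, and sensitivity and specificity with CIs at one parameter and cut-off per method, fixed before FFR is linked to the imaging data. Keep correlations as descriptive.
- Give the paired (DeLong) difference in AUC as an estimate with a CI, not as a superiority test. State that it applies only to side branches with DS below 70%, TIMI 3 flow and no dissection, and that this selection can lower the AUC of the angiographic measure more than that of 3D-OCT. Report how many patients have FFR.
- Add Bland-Altman bias and limits of agreement only for quantities that both methods measure in the same units, such as percent stenosis of the side-branch ostium.

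The cost is a little more analysis on data already planned, with no added procedures or patients. The downside is modest precision, which the intervals will show.
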